3.6 Summaries to Support the Secondary Objectives

The secondary objectives of this study are:

1) To evaluate the safety and tolerability of tralokinumab.

- 2) To evaluate the effect of tralokinumab on pulmonary function: clinic spirometry, including pre- and post-bronchodilator FEV1, FEV6, FVC, FEV1/FVC, IC; and PEF and FEV1 measured at home.
- 3) To evaluate the effect of tralokinumab on Patient Reported Outcomes: ACQ-6 score, HRQoL using AQLQ[S], and EQ-5D.
- 4) To evaluate the effect of tralokinumab on asthma symptoms and use of rescue medication using the ASMA diary.
- 5) To describe the pharmacokinetics (PK) and immunogenicity of tralokinumab.

3.6.1 Safety and Tolerability of Tralokinumab

3.6.1.1 Adverse Events

Adverse events (AE) and serious adverse events (SAE) will be summarized by system organ class, preferred term, severity, and relationship to investigational product. Special information regarding diarrhea and urinary AE is collected through questionnaire in the study. The diarrhea questionnaire and urinary AE questionnaire will be summarized with descriptive statistics.

Injection site reactions are considered an AE of interest for analysis. The Preferred Terms to be included under the definition of "injection site reaction" are outlined in the table below (124 terms). These will be summarized for the overall safety population by cohort and by treatment group.

AE of interest	MedDRA (version 15.1) Preferred Terms
Injection Site Reactions	Administration site abscess, administration site infection, administration site pain, administration site rash, administration site reaction, application site abscess, application site alopecia, application site anaesthesia, application site atrophy, application site burn, application site cellulitis, application site cold feeling, application site dermatitis, application site discharge, application site discolouration, application site discomfort, application site dryness, application site eczema, application site erosion, application site erythema, application site exfoliation, application site fissure, application site folliculitis, application site

Version 2.0

haematoma, application site haemorrhage, application site hyperaesthesia, application site hypersensitivity, application site induration, application site infection, application site inflammation, application site irritation, application site mass, application site necrosis, application site nodule, application site odour, application site oedema, application site pain, application site pallor, application site papules, application site paraesthesia, application site perspiration, application site photosensitivity reaction, application site pruritus, application site pustules, application site rash, application site reaction, application site scab, application site scar, application site swelling, application site telangiectasia, application site ulcer, application site urticaria, application site warmth, application site vesicles, injection site abscess, injection site abscess sterile, injection site anaesthesia, injection site atrophy, injection site calcification, injection site cellulitis, injection site coldness, injection site cyst, injection site dermatitis, injection site discharge, injection site discolouration, injection site discomfort, injection site dryness, injection site dysaesthesia, injection site eczema, injection site erosion, injection site erythema, injection site exfoliation, injection site extravasation, injection site fibrosis, injection site granuloma, injection site haematoma, injection site haemorrhage, injection site hypersensitivity, injection site hypertrophy, injection site induration, injection site infection, injection site inflammation, injection site injury, injection site irritation, injection site ischaemia, injection site laceration, injection site lymphadenopathy, injection site macule, injection site mass, injection site movement impairment, injection site necrosis, injection site nerve damage, injection site nodule, injection site oedema, injection site pain, injection site pallor, injection site papule, injection site paraesthesia, injection site phlebitis, injection site photosensitivity reaction, injection site pruritus, injection site pustule, injection site rash, injection site reaction, injection site recall reaction, injection site scab, injection site scar, injection site streaking, injection site swelling, injection site

MedImmune

Tralokinumab

Version 2.0

	thrombosis, injection site ulcer, injection site urticaria, injection
	site warmth, injection site vasculitis, injection site vesicles,
	malabsorption from injection site, puncture site abscess, puncture
	site discharge, puncture site haemorrhage, puncture site
	induration, puncture site infection, puncture site pain, puncture
	site reaction, puncture site swelling

Adverse events may be treatment emergent (i.e., occurring after initial receipt of investigational product) or nontreatment emergent. A nontreatment-emergent AE is any new sign or symptom, disease, or other untoward medical event that begins after written informed consent has been obtained but before the subject has received investigational product.

Adverse event that do not have a valid onset date and where it cannot be ascertained whether the onset date is on or after the first dosing date will be counted as treatment emergent AE (TEAE) and will be included in AE summary tables.

- 1. For AE with valid onset year and month but missing onset day, (1) if the year of onset date is greater than the year of first dosing date, then the AE is TEAE; (2) if the year of onset is equal to the year of first dosing and the month of the onset is greater than the first dosing date, then the AE is TEAE; (3) if the year and month of onset are equal to the year and month of first dosing date and (the AE stop date is after the date of first dosing date or AE stop date is missing or continuing), then the AE is TEAE.
- 2. For AE with valid onset year but missing onset month and day, (1) if the year of onset is greater than or equal to the year of first dosing date, then the AE is TEAE; (3) if the year of onset is equal to the year of first dosing date and (the AE stop date is after the first drug dosing or AE stop date is missing or continuing), then the AE is TEAE.
- 3. For AE with completely missing onset date, if the AE stop date is less than the date of first dosing, then the AE is non-emergent AE; otherwise, count it as TEAE.

Summary	Population	Analysis
Number of Subjects with Non-Treatment Emergent Adverse Events	Safety	Stage 2
Rate Summary of Non-Treatment Emergent Adverse Events	Safety	Stage 2

Version 2.0

Number of Subjects with Treatment Emergent Adverse Events	Safety	Stage 1; Stage 2
Rate Summary of All Treatment Emergent Adverse Events	Safety	Stage 2
Number of Subjects with Treatment Emergent Adverse Events by Highest Severity	Safety	Stage 1; Stage 2
Number of Subjects with Treatment Emergent Adverse Events Sorted by Frequency	Safety	Stage 1; Stage 2
Number of Subjects with Related Treatment Emergent Adverse Events	Safety	Stage 1; Stage 2
Number of Subjects with Related Treatment Emergent Adverse Events by Highest Severity	Safety	Stage 1; Stage 2
Number of Subjects with Non-Treatment Emergent Serious Adverse Events	Safety	Stage 2
Number of Subjects with Treatment Emergent Serious Adverse Events	Safety	Stage 1; Stage 2
Number of Subjects with Treatment Emergent Serious Adverse Events by SAE Criteria	Safety	Stage 1; Stage 2
Number of Subjects with Related Treatment Emergent Serious Adverse Events	Safety	Stage 1; Stage 2
Number of Subjects with Treatment Emergent Serious Adverse Events by Highest Severity	Safety	Stage 1; Stage 2
Non-Treatment Emergent Adverse Events Resulting in Death	Safety	Stage 1; Stage 2
Treatment Emergent Adverse Events Resulting in Death	Safety	Stage 1; Stage 2
Number of Subjects with Treatment Emergent Adverse Events Resulting in Permanent Discontinuation of Study Drug	Safety	Stage 1; Stage 2
Summary of Diarrhea Questionnaire	Safety	Stage 1; Stage 2

Summary of Urinary AE Questionnaire	Safety	Stage 1; Stage 2
Summary of Injection Site AEs	Safety	Stage 1; Stage 2

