Subjects will continue to receive the same fixed-dose combination product of fluticasone/salmeterol with or without additional asthma controller medications at a stable dose during the treatment period and through Week 53. Subjects who experience an asthma

Version 2.0

exacerbation during the treatment period will be treated accordingly and will remain in the study.

Subjects will return to the clinic at Week 53 for an assessment of the efficacy endpoints. Subjects will have 3 additional follow-up visits at Weeks 59, 67, and 75. After the Week 53 visit, background medications may be changed as deemed necessary by the investigator.

As part of the study, selected sites will take part in a substudy using HRCT scanning to measure potential airway wall structural changes including airway wall thickness. Sites will be selected on their ability and willingness to carry out the scans. Participation in this substudy is optional for subjects at the selected sites. An adequate number of sites will be identified in order to target recruitment of approximately 40 subjects into each of the 2 treatment groups for the HRCT substudy.

[figure not shown]

Figure 2.1-1 Study Flow Diagram

Q2W = every 2 weeks; Q4W = every 4 weeks; Wks = Weeks

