3.1 General Considerations

Two formal analyses (Stage 1 analysis and Stage 2 analysis) as well as an interim analysis are planned for the study.

The Stage 1 analysis for the overall population will be conducted after the last non-Japanese subject has completed the Week 53 visit or discontinued prematurely (this analysis will include all Japanese subjects who have completed Week 53). The Stage 2 analysis for long-term safety follow-up will be performed after all subjects have completed the study or discontinued prematurely. During the Stage 1 analysis, all the efficacy and safety data

Version 2.0

collected will be analyzed. Pairwise comparisons between individual tralokinumab treatment groups and combined placebo will be conducted. The primary analysis for which the study is powered will be completed in the Stage 1 analysis, and the analyses based on primary efficacy endpoint will be repeated for overall population (which includes all subjects enrolled into the study) at the end of the study as sensitivity analysis.

The interim analysis will be conducted after the last non-Japanese subject randomized into the study has completed the Week 39 visit or discontinued prematurely. All data available will be analyzed as part of the interim analysis. The details of the interim analysis will be specified in unblinding plan for interim analysis.

The overall type I error rate (two-sided) will be controlled at the 0.15 level using O'Brien-Fleming alpha spending function based on the actual person-years follow-up observed. For example, if the information fraction at the interim analysis is 88%, then the two-sided type I error rate will be 0.105 for the interim analysis and 0.128 for final analysis, respectively. The interim analysis will have minimal impact on the power of the study at the final analysis, which is estimated to be approximately 78%.

Three sets of analyses will be performed at Stage 1. They are: 1) analyses based on overall population; 2) analyses for Japan only subjects (n=45); and 3) analyses for non-Japanese subjects. The go/no-go decision will be based on stage 1 analysis for overall population.

In addition, for PMDA consultation, the same analyses for all Japan subjects (n=64) will be conducted when all Japan subjects complete week 53 follow-up or discontinue prematurely.

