The crude asthma exacerbation rate will be estimated as a weighted mean (total number of exacerbations for the treatment group divided by the total duration of person follow-up) per the joint guidelines recommended by the ATS/ERS. The primary endpoint analysis will be conducted based on the ITT population using a Poisson regression model adjusted for overdispersion (Pearson Chi-Square correction) with treatment group, age, gender (male vs female), number of asthma exacerbations in the past year ($2 \text{ vs} > 2 \text{ but} \le 6 \text{ exacerbations}$), atopic asthma status (atopic vs. non-atopic), chronic OCS use (presence versus absence), and geographical region (United States/Canada/Western Europe, Eastern Europe, Asia, rest of world) as covariates and the log of number of days in the study as offset. Exacerbation rates, 85% CIs, rate ratios, 2-sided p-values will be provided based on the Poisson regression model. The primary endpoint will also be analyzed using a negative binomial regression model to assess the robustness with regard to the distributional assumptions. Pairwise comparisons between individual tralokinumab treatment group and combined placebo from Cohorts 1 and 2 will be conducted. Comparison between tralokinumab and placebo from the same cohort will be conducted as secondary analyses. Analysis based on the PP population will be performed as a sensitivity analysis.

The primary endpoint will also be analyzed using Cochran-Mantel-Haenszel row Mean Score Test. For analyses based on ITT Population, the adjusted number of exacerbations for subjects who withdraw from the study will be calculated using the following equation: [recorded number of exacerbations] / [number of days in the study] × 365.25.

Severe asthma exacerbations are of interest. The Analyses mentioned above will be conducted specifically for severe asthma exacerbations as well.

In addition, asthma exacerbations and severe asthma exacerbations between week 53 and end of the study, and asthma exacerbations and severe asthma exacerbations through the end of the study will also be summarized. Time to first exacerbation and time to first severe exacerbation will be analyzed as a supportive efficacy analysis to the primary objective. A Cox proportional hazard model will be fitted to data.

The number and proportion of subjects with different number of asthma exacerbations and severe asthma exacerbations (0, 1, 2, 3, and > 3) will be summarized by treatment group.

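### The only treatment-emergent adverse event rate table pools the treatment period with follow-up to Week 75, and no adverse event table shows either period separately

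*SAP*

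**What the plan says.** Section 3.6.1.1 opens the treatment-emergent window at first dose: "Adverse events may be treatment emergent (i.e., occurring after initial receipt of investigational product) or nontreatment emergent". The complementary category is an event that "begins after written informed consent has been obtained but before the subject has received investigational product". Between them, every event after first dose is treatment emergent, however long after the last dose it starts.

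The summary table in the same section lists two rate tables, both at Stage 2 only: "Rate Summary of All Treatment Emergent Adverse Events" and "Rate Summary of Non-Treatment Emergent Adverse Events". Most subject-count tables, such as "Number of Subjects with Treatment Emergent Adverse Events by Highest Severity", run at Stage 1 and Stage 2. None carries a period label.

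On Stage 2, section 3.1 says: "The Stage 2 analysis for long-term safety follow-up will be performed after all subjects have completed the study or discontinued prematurely". Stage 1 takes place once the last non-Japanese subject has reached Week 53 or left, and it uses all efficacy and safety data collected by then.

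Section 2.1 places follow-up visits at Weeks 59, 67 and 75 and adds: "After the Week 53 visit, background medications may be changed as deemed necessary by the investigator". For efficacy, section 3.5 does separate the periods. It plans a summary of "asthma exacerbations and severe asthma exacerbations between week 53 and end of the study", alongside tables through Week 53 and through the end of the study.

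**The concern.** Safety is the first secondary objective in section 3.6. The time before and after Week 53 differs in study drug and possibly in background medication. If the two are pooled, an excess that belongs to one period is averaged with time in which it may be absent.

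A reader of the report would want two answers: how the regimens compare with placebo while subjects are being treated, and whether anything emerges after treatment stops. No planned adverse event table is built to give either. Stage 2 is described as the long-term safety follow-up analysis, yet its treatment-emergent tables accumulate from first dose and do not show that follow-up by itself.

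**Working it through.** **1. Dosing and off-drug time (section 2.1, first dose at Week 1).**
- Cohort 1: 50/2 + 1 = 26 doses, which matches the SAP. The last dose falls at Week 51.
- Cohort 2: 12/2 + 1 = 7 doses to Week 13, then 9 four-weekly doses from Week 17 to Week 49. The total is 16, which matches the SAP.
- Observation: 75 − 1 = 74 weeks.
- After the Week 53 visit: 75 − 53 = 22 weeks, and 22/74 = 30%.
- After the last scheduled dose: 75 − 51 = 24 weeks (Cohort 1) and 75 − 49 = 26 weeks (Cohort 2).

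**2. Effect of pooling on a person-time rate ratio.** Assume a constant placebo rate, complete follow-up, and an effect confined to one period.
- Excess confined to the period to Week 53: pooled ratio = (52 × RR + 22)/74.
- Excess confined to follow-up: pooled ratio = (52 + 22 × RR)/74.

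| True ratio in the affected period | Pooled, excess to Week 53 only | Pooled, excess in follow-up only |
|---|---|---|
| 1.5 | 100/74 = 1.35 | 85/74 = 1.15 |
| 2.0 | 126/74 = 1.70 | 96/74 = 1.30 |
| 3.0 | 178/74 = 2.41 | 118/74 = 1.59 |

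If the effect instead stops at the last dose, a ratio of 2.0 appears as (50 × 2 + 24)/74 = 1.68 in Cohort 1 and (48 × 2 + 26)/74 = 1.65 in Cohort 2. If it persists at 2.0 for half of follow-up (11 weeks), it appears as (63 × 2 + 11)/74 = 1.85.

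**3. Subject-count tables.** Take assumed risks to Week 53 of 10% and 5%, with both arms at the placebo hazard afterwards.
- Placebo by Week 75: 1 − 0.95^(74/52) = 7.0%.
- Active by Week 75: 1 − 0.90 × 0.95^(22/52) = 11.9%.
- The risk ratio falls from 2.0 to 1.70. The risk difference moves only from 5.0 to 4.9 points.

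**4. Can Stage 1 stand in for the treatment period?** Stage 1 is a calendar cut, so early recruits already have follow-up data. With uniform accrual over A weeks (A is an assumption), mean time after Week 53 among those still in the study is (22²/2 + 22 × (A − 22))/A:
- A = 26: 12.7 weeks
- A = 52: 17.3 weeks
- A = 78: 18.9 weeks

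The populations differ too. Section 3.1 gives 45 Japanese subjects at Stage 1 and 64 in all, so Stage 2 adds treatment-period data for 64 − 45 = 19 subjects. Subtracting Stage 1 from Stage 2 therefore does not isolate follow-up.

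**The case against.** Counting everything from first dose to the end of the study is a common, inclusive convention. It drops no late event, and planned follow-up is equal across arms. That stands: the definition is not an error, and the cumulative tables should stay.

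The arithmetic depends on things the SAP does not state. It gives no denominator for the rate, and nothing in it says that a drug effect ends at Week 53; anti-drug antibodies are still measured at Weeks 59 and 75 (section 3.6.4). This also stands, so the ratios are conditional illustrations.

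A reader might infer that harm in follow-up cannot be seen at all. The SAP does not support that. Section 3.1 provides listings by treatment group, subject and visit, laboratory results are summarised by time point, and exacerbations after Week 53 have their own tables. Events leading to discontinuation of study drug belong to treatment by construction, and injection site reactions are largely tied to dosing. What is missing is a tabulated comparison by period with its own person-time.

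Stage 1 might be meant to stop at Week 53, as it does where tables in sections 3.3, 3.5 and 3.6.2 carry that label. The adverse event tables carry no such label, and section 3.1 points to all data collected, so the text does not establish a Week 53 cut.

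The separate programming plan may hold denominators and templates. It is not shown. Even so, the SAP itself lists its adverse event summaries by stage, and it names periods for exacerbations rather than leaving them to that plan.

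**Conclusion.** The point holds as a worthwhile, inexpensive improvement. The treatment-emergent window has no stated end, the single treatment-emergent rate table pools treatment with follow-up, and no adverse event table separates the two, although the SAP does so for exacerbations.

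The size is conditional. With a person-time rate, complete follow-up, a constant background rate and an excess confined to one side of Week 53, a ratio of 2.0 appears as about 1.70 (treatment period only) or 1.30 (follow-up only). Risk differences in count tables are almost unaffected, and persistence of effect after dosing weakens the dilution.

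Two stronger readings should be avoided. This is not the only adverse event rate table, since one for events before first dose also exists. And 22 weeks is time after the Week 53 visit, not time off drug, which is about 24 to 26 weeks from the last scheduled dose.

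**What to change.** Keep the cumulative treatment-emergent tables. In section 3.6.1.1, state the rate denominator and add runs of the treatment-emergent, serious and rate tables for two periods, each with its own person-time:

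- **(a)** first dose to the Week 53 visit, or to leaving the study if earlier, at Stage 1 and Stage 2;
- **(b)** after the Week 53 visit to the end of the study, at Stage 2.

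Assign each event by onset date. Events that start after a subject stops drug early but before Week 53 then stay in period (a), and none falls between the periods. Label (a) as the period to Week 53 rather than as on-drug time, because it includes the weeks after the last dose and any time after early stopping.

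The cost is SAP wording and a few extra table runs. Counts in period (b) will be sparse and should be read descriptively. No new data are needed.

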2.1 Study Overview

This is a Phase 2b, randomized, double-blind, placebo-controlled, parallel-arm, multicenter study to evaluate the efficacy and safety of two SC treatment regimens of tralokinumab in adult subjects with uncontrolled, severe asthma requiring high-dose ICS and LABA with or without additional controller medications (high-dose ICS defined as a total daily dose $> 500 \mu g$ fluticasone DPI or $> 440 \mu g$ MDI; GINA, 2009; National Heart, Lung, and Blood Institute, 2007). Approximately 100 sites around the world will participate in the study. A total of approximately 390 subjects will be randomized in a 1:1 ratio to one of 2 cohorts (Cohort 1 or Cohort 2). Within each cohort, subjects will be randomized in a 2:1 ratio to receive tralokinumab (300 mg) or placebo as follows:

Cohort 1: Tralokinumab 300 mg (n = 130) or Placebo (n = 65) as 2 SC injections Q2W for 50 weeks for a total of 26 doses

Cohort 2: Tralokinumab 300 mg (n = 130) or Placebo (n = 65) as 2 SC injections Q2W for 12 weeks followed by Q4W for 38 weeks for a total of 16 doses

Subjects will be stratified at screening by the number of asthma exacerbations in the past 12 months (2 versus > 2 but \leq 6 exacerbations) and by chronic OCS use (presence versus absence). To maximize the probability of obtaining treatment balance within Japanese population for the purpose of PMDA filing, the Japanese will be randomized separately.

A 5-week screening/run-in period (Week -5 to -1 [Day -1) will precede investigational product administration. Starting at Week -4 (Day -28), subjects will receive a fixed-dose combination product of fluticasone/salmeterol, either as an MDI (230 μ g/21 μ g) at a dose of 2 inhalations twice per day or as a DPI (500 μ g/50 μ g) at a dose of one inhalation twice per day. Sites/subjects will be permitted to use either presentation of fluticasone/salmeterol if approved and available for use in their country. If the subject is also taking additional asthma controller medications (including leukotriene modifiers, theophylline, chromones, or OCS \leq 20 mg/day), then these medications should be continued at a stable dose during the screening/run-in period. During the study, subjects may use inhaled reliever therapy (e.g., SABA or short-acting anticholinergic) on an as-required basis as documented in their Personalized Asthma Action Plan.

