3.2.3 Safety Population

The safety population includes all subjects who receive any investigational product and have safety data available. The safety analyses will be presented on an 'as-treated' basis.

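### The treatment-emergent definition has no worsening clause, so a fully dated run-in event that worsens or turns serious on treatment stays out of the treatment-emergent tables unless it is recorded as a new event

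*SAP*

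**What the plan says.** SAP 3.6.1.1 divides adverse events into two classes: "Adverse events may be treatment emergent (i.e., occurring after initial receipt of investigational product) or nontreatment emergent". The nontreatment-emergent class is any event "that begins after written informed consent has been obtained but before the subject has received investigational product".

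Three numbered rules then deal with partial or missing onset dates. The general default is that an event "where it cannot be ascertained whether the onset date is on or after the first dosing date will be counted as treatment emergent AE". Under the rule for a missing onset day in the month of first dosing, the event is treatment emergent if "the AE stop date is after the date of first dosing date or AE stop date is missing or continuing".

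The table list in 3.6.1.1 gives the breakdowns by highest severity, relatedness, SAE criteria and stopping of study drug for treatment-emergent events only; the last of these is "Number of Subjects with Treatment Emergent Adverse Events Resulting in Permanent Discontinuation of Study Drug". Nontreatment-emergent events have four summaries of their own: a count and a rate summary (Stage 2), "Number of Subjects with Non-Treatment Emergent Serious Adverse Events" (Stage 2), and a table of events with a fatal outcome (Stages 1 and 2). All of these use the Safety population, which SAP 3.2.3 defines as follows: "The safety population includes all subjects who receive any investigational product and have safety data available".

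On the pre-dose window, SAP 2.1 says: "A 5-week screening/run-in period (Week -5 to -1 [Day -1) will precede investigational product administration".

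**The concern.** Both definitions turn on when the event starts. What happens to it after dosing plays no part. A mild event that begins in run-in and becomes severe or serious on study drug therefore keeps its pre-dose label.

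Such events are foreseeable. The window lasts five weeks, and SAP 2.1 has subjects start the fixed-dose fluticasone/salmeterol product at Week -4. Randomisation should balance the run-in events themselves between arms, but it does not fix their course afterwards. That course is a possible effect of treatment, and the treatment-emergent tables are where the arms are compared on it. Safety and tolerability is the first secondary objective (SAP 3.6). Stage 1, which carries the go/no-go decision (SAP 3.1), is where the gap for serious events is widest.

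**Working it through.** No arithmetic applies: the plan states no figure that depends on this rule. The check is to apply the rule to a subject who is later dosed and whose event has a complete onset date in run-in, and to follow the event through the table list in SAP 3.6.1.1.

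1. **Severity rises after dosing.** The event began before the first dose, so it is nontreatment emergent. It is absent from every treatment-emergent table, including those by highest severity and relatedness. It appears only in the nontreatment-emergent count and rate summaries, at Stage 2, where severity is not shown.
2. **Becomes serious after dosing.** It is absent from all treatment-emergent SAE tables. Its only SAE table is the nontreatment-emergent one, which is Stage 2 only. It is therefore in no Stage 1 SAE table.
3. **Proves fatal after dosing.** It is shown at Stages 1 and 2, but in the nontreatment-emergent death table.
4. **Leads to permanent stopping of study drug.** It is absent from the discontinuation table, which has no nontreatment-emergent counterpart. The subject can still be counted under the adverse-event reason in the end-of-treatment status summary (SAP 3.3, ITT, Stage 1), but nothing in the SAP says that the event term is shown there.

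Case 3 also tests whether this reading is the intended one. The Safety population contains only dosed subjects. Anyone in it with a fatal nontreatment-emergent event had an event that began before dosing and died after dosing. The plan provides a table for exactly this case and keeps the pre-dose label, so a later change in the event does not move it across.

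A comparison of two date situations shows that the rule is uneven. Take an event that began in the calendar month of the first dose, before that dose, and was still ongoing after it. If the onset day is missing, rule 1(3) makes it treatment emergent. If the full date is recorded, it is nontreatment emergent, even if it then becomes serious. Doubtful dates are resolved conservatively, while documented worsening on treatment is not counted.

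**The case against.** The strongest objection is that the protocol or the CRF instructions may require a worsening to be entered as a new adverse event with its own onset date. The worsening would then begin after dosing and be treatment emergent, and nothing would be lost. That is a recording rule a SAP often leaves elsewhere. The objection makes the size of the gap conditional, but it does not remove the gap: the SAP sets the classification itself and neither states nor relies on such a convention.

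Several stronger readings are tempting, and the document does not support them.

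- *That these events vanish from safety reporting.* They do not. The nontreatment-emergent AE and SAE tables exist at Stage 2 and the death table at both stages, and SAP 3.1 presents summaries by treatment group. Laboratory, vital-sign and ECG shift tables, and the exacerbation endpoint, also capture some worsening whatever the AE onset.
- *That onset date alone decides every case.* This holds only for complete onset dates. With partial or missing dates the stop date is used, and unresolved cases default to treatment emergent.
- *That the disposition and discontinuation tables contradict each other.* The first is ITT and the second is Safety on an as-treated basis, so they need not agree under any definition.
- *That the loss is of a known size, falls mainly on serious or drug-stopping events, or differs by arm.* No passage gives a figure or evidence for any of these.

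It is also fair to say that stopping study drug, with no worsening, is not in itself a reason to call a pre-dose event treatment emergent.

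**Conclusion.** The point holds in a limited form. For adverse events with a complete onset date, SAP 3.6.1.1 makes no provision for worsening after dosing. If worsening is not recorded as a new event, run-in events that increase in severity or become serious on treatment are left out of all treatment-emergent tables. The consequences that matter most are the absence of such serious events from every Stage 1 SAE table, and the lack of any nontreatment-emergent breakdown by severity, relatedness or discontinuation.

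The direction is an undercount of on-treatment harm in the treatment-emergent tables. The size cannot be computed: it depends on how many subjects are dosed with a run-in event still present and how many of those events worsen, and the SAP gives neither. The conclusion rests on the SAP text and on the assumption that no recording convention elsewhere already turns worsening into a new event. Efficacy, alpha and power are not touched. The change is worth making because it is cheap and because the rule is stated, not merely left open.

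**What to change.** In SAP 3.6.1.1, define a treatment-emergent adverse event as one with onset at or after the first dose, or with onset before the first dose that increases in severity or becomes serious after the first dose. Alternatively, if the protocol or CRF instructions already provide for it, state that such worsening is recorded and analysed as a new adverse event with its own onset date. Apply the chosen rule to every treatment-emergent table at Stages 1 and 2.

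Do not relabel pre-dose events that lead to stopping study drug without worsening. Show them in the Stage 1 discontinuation table as a separate nontreatment-emergent row.

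The cost is a sentence or two of text, one derivation, one extra table row and slightly higher treatment-emergent counts. There is one practical limit: if the CRF holds only the highest severity of an event, a post-dose rise in severity cannot be dated, and only the change to serious can be. The SAP should then say so.
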